2.2 Endpoint Analyses

2.2.1 Primary Endpoint Analysis

Primary Analysis:

A non-inferiority test will be performed on the primary endpoint between 1-month and 6-month follow up for the primary analysis population of the 1-month DAPT arm and the XIENCE V USA historical control stratified by propensity score quintiles as described in section 2.1.4.

To ensure all subjects to be included in this analysis, multiple imputations will be performed in calculating the propensity scores.

Secondary Analysis (as a sensitivity analysis):

In addition to the primary analysis stratified by propensity score quintile, a non-inferiority test will be performed on the primary endpoint stratified by propensity score quartile, with the same methodology as described above.

2.2.3 Secondary Endpoint Analyses

The secondary clinical endpoints will be descriptively analyzed for both the primary analysis population and all registered subjects without propensity stratification.

2.3 Subgroups for Analysis

All of the following subgroup analyses are intended for the primary analysis population. The comparison between the 1-month DAPT arm and the XIENCE V USA historical control will be analyzed descriptively within each quintile for the primary in a specific subgroup. The above quintiles are based on the overall PS, not PS built within each subgroup, as baseline characteristics of subjects are likely to be comparable in each quintile of the overall PS.

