1.5 Sample Size Calculations

[REDACTED]

[REDACTED]

[REDACTED]

[REDACTED]

[REDACTED]

[REDACTED]

[REDACTED]

- Sample size in the control arm (1-month clear): ~1,400

[REDACTED]

A sample size of approximately 800 subjects in the 1-month DAPT arm will be required for this test.

[REDACTED]

[REDACTED]

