2.1.3 Propensity Score

Given that subjects in the two comparison groups (the 1-month DAPT arm vs XIENCE V USA historical control) are not randomized and thus may not have balanced baseline characteristics, the non-inferiority and superiority tests for 1-6 month period will be carried out through stratified analysis in the “1-month clear” population. The stratification will be performed through propensity scores (PS). For each individual a propensity score (i.e., predicted probability between 0 and 1) for group (1-month DAPT arm) membership will be calculated using logistics regression, with “group” as the outcome and baseline variables including demographic, lesion characteristics, and risk factors as the predictors. Subjects will be categorized into 5 groups based on the calculated propensity scores and their quintiles. Non-inferiority and superiority will then be carried out for the rate of the endpoint using the method described in sections below stratified by the propensity quintiles.

The propensity score modeling and design will be performed by an independent statistician who has no access to any outcome data of the XIENCE 28 Global study and the XIENCE V USA historical control for the integrity and interpretability of study results. The independent statistician will be blinded and have no access to clinical outcome and any follow-up information to avoid introducing bias into the analysis. [REDACTED]

2.1.3-1 Propensity Score Variable List

Based on prior clinical experience and clinical research, below is the list of variables that are considered to be related to assignments modeling building:

- Gender
- Age
- Creatinine
- Chronic anticoagulant
- History of stroke
- History of major bleeding
- Platelet
- Hb
- BMI
- Hypertension
- Dyslipidemia
- Prior PCI
- Prior CABG
- Prior MI
- Multivessel disease
- Clinical presentation (ACS (NSTEMI, ACS unstable angina) vs. non-ACS)
- Diabetes
- ACC/AHA lesion complexity

- Total lesion length per patient
- RVD
- Diameter stenosis%
- Bifurcation
- Number of lesions treated
- Number of vessels treated
- Number of stents per patient
- Total stent length per patient
- Discharge P2Y12
- Paris bleeding score
- PRECISE DAPT score

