2.1.4 Hypothesis Testing

Primary endpoint analysis for 1-month DAPT

[figure not shown]
The XIENCE 28 Global study is powered based on primary endpoint of NACE between 1-month and 6-month follow-up. NACE is defined as the composite rate of all-cause death, all myocardial infarction (modified Academic Research Consortium [ARC]), stent thrombosis (ARC definite or probable), stroke or major bleeding (Bleeding defined by the Bleeding Academic Research Consortium [BARC] type 2-5) from 1 to 6 months. This primary endpoint will be evaluated between 1-month DAPT arm and XIENCE V USA historical control stratified by propensity score quintiles in the primary analysis population. The null (H_0) and alternative (H_A) hypothesis are of the following form:

$$H_0: NACE_{1m-DAPT} - NACE_{Xience\ V\ USA} \geq \delta$$

$$H_A: NACE_{1m-DAPT} - NACE_{Xience\ V\ USA} < \delta$$

Where δ is the non-inferiority margin. The test will be carried out with a one-sided significance level of 0.05 and a non-inferiority margin (δ) of 4.0%.

The stratified Farrington-Manning method will be performed to test non-inferiority (NI) of 1-month DAPT compared to standard DAPT duration from XIENCE V USA historical control.

[REDACTED]

[REDACTED]

[REDACTED]

[REDACTED]

[REDACTED]

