2.3.1 Sex

Sex-specific subgroup analyses will be performed on the primary analysis population for the primary endpoint stratified by the overall PS.

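### SAP 2.3 has subgroups described quintile by quintile, and the visible text specifies no subgroup difference combined over quintiles and no comparison between levels

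*SAP*

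**What the plan says.** - SAP 2.3 states the method for all subgroups: the comparison with the XIENCE V USA control "will be analyzed descriptively within each quintile for the primary in a specific subgroup". The quintiles are those of the overall propensity score, not of scores rebuilt inside each subgroup.
- SAP 2.3.1 (sex) words it differently: the analysis is "for the primary endpoint stratified by the overall PS". SAP 2.3.2 (diabetes) and 2.3.3 (age at the median, and clinical presentation at three levels) use the same phrase.
- SAP 2.1.3 defines the strata: "Subjects will be categorized into 5 groups based on the calculated propensity scores and their quintiles".
- SAP 1.5 gives the sizes: "A sample size of approximately 800 subjects in the 1-month DAPT arm will be required for this test", and "Sample size in the control arm (1-month clear): ~1,400".
- SAP 2.1.2 provides Newcombe 95% intervals for a difference of two percentages where such a difference is specified.
- Protocol 9.4.3 lists sex, diabetes and age, followed by a redacted block. SAP 2.3 to 2.3.3 show no redaction.

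**The concern.** A subgroup analysis of the primary endpoint serves to show whether the result is broadly consistent across kinds of patient. Under the sentence in SAP 2.3, each level is split again into five quintiles and the arms are compared inside each. That gives five imprecise differences per level, with no stated rule for combining them and no stated comparison between levels. The phrase in 2.3.1 to 2.3.3 can be read as a single stratified analysis, so two programmers could produce different tables from the same plan.

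At stake is the readability of an exploratory display. Five noisy differences can easily look inconsistent by chance, while the precision that the same strata would give in combination goes unused.

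**Working it through.** **Inputs from the documents.** About 800 trial subjects and 1,400 controls (SAP 1.5); five strata (SAP 2.1.3); for scale, the primary test has a "one-sided significance level of 0.05 and a non-inferiority margin (δ) of 4.0"% (SAP 2.1.4).

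**The plan's own figure.** The documents give no subgroup precision to reproduce. The inputs behind the 800 are redacted. With 800 against 1,400, the 4.0-point margin and one-sided 0.05, the normal approximation gives power of 99.4%, 95.4%, 91.4%, 87.1% and 81.1% at common rates of 5%, 8%, 10%, 12% and 15%. Many event rates could therefore fit.

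**Assumptions (not in the documents).** Common NACE rate p of 5% to 12%; subgroup share s of 35% or 50%, the same in every quintile; propensity predictors 1 SD apart between the groups. That separation spreads subjects over quintiles 1 to 5 as follows:
- trial arm a: 46, 95, 146, 208, 305
- control b: 394, 345, 294, 232, 135

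**Formulas.** Within quintile k: half-width = 1.96 × √[p(1−p)(1/(s·a) + 1/(s·b))]. Pooled with Mantel-Haenszel weights w = ab/(a+b): half-width = 1.96 × √[p(1−p)/(s·Σw)]. The weights are 41.2, 74.5, 97.6, 109.7 and 93.6, so Σw = 416.5.

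**Worked case, s = 35%, p = 10%.** Quintile 1 has 46 × 0.35 = 16.1 trial subjects and 394 × 0.35 = 137.9 controls. It expects 1.6 trial events, and its half-width is 1.96 × √[0.09(1/16.1 + 1/137.9)] = 15.5 points. Pooled: 1.96 × √[0.09/(0.35 × 416.5)] = 4.9 points.

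| Share | Rate | 95% half-width in quintiles 1 to 5 (points) | Pooled (points) | Trial events expected in quintile 1 | Cells of 10 expecting fewer than 4 events |
|---|---|---|---|---|---|
| 50% | 5% | 9.4, 7.0, 6.1, 5.8, 6.2 | 3.0 | 1.2 | 4 |
| 50% | 10% | 13.0, 9.6, 8.4, 7.9, 8.6 | 4.1 | 2.3 | 1 |
| 50% | 12% | 14.0, 10.4, 9.1, 8.6, 9.3 | 4.4 | 2.8 | 1 |
| 35% | 5% | 11.3, 8.4, 7.3, 6.9, 7.5 | 3.5 | 0.8 | 5 |
| 35% | 10% | 15.5, 11.5, 10.1, 9.5, 10.3 | 4.9 | 1.6 | 2 |
| 35% | 12% | 16.8, 12.5, 10.9, 10.3, 11.1 | 5.3 | 1.9 | 2 |

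**Gain from pooling.** The ratio of pooled to within-quintile width is √(w/Σw). It runs from √(41.2/416.5) = 0.31 in quintile 1 to √(109.7/416.5) = 0.51 in quintile 4, and it depends on neither p nor s.

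**Sensitivity to overlap.** With both groups spread evenly (160 and 280 per quintile) the ratio is 1/√5 = 0.45. A 50% subgroup then has within-quintile half-widths of 6.0 to 8.9 points at rates of 5% to 12%, and a 15% subgroup 10.9 to 16.3 points. All exceed 4.0 points.

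**Difference between levels, p = 10%, 1 SD separation.** At 50:50, √(4.07² + 4.07²) = 5.8 points. At 35:65, √(4.87² + 3.57²) = 6.0 points.

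**Chance inconsistency.** With identical true rates in both groups and the 1 SD spread, a 35% subgroup at 8% shows at least one quintile difference beyond 4 points in 94% of simulated trials, and differences beyond 4 points in opposite directions in 46%. For a 50% subgroup at 5% the figures are 80% and 23%.

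**The case against.** A reader might infer that subgroup cells in general hold only one to a few events, and that the plan can yield no usable subgroup or interaction estimate. The documents do not support either statement.

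- **Cell counts.** At a 10% rate and a 35% share, 2 of the 10 cells expect fewer than 4 events; at a 50% share, 1 does. Very low counts belong mainly to the lowest trial-arm quintiles, low event rates and small subgroups. The rates and shares are not public, so no count can be fixed from the documents.
- **Usable estimate.** The phrase "primary endpoint stratified by the overall PS" is close to the wording for the primary analysis, which is a single stratified test. SAP 2.3.1 to 2.3.3 can therefore be read as a combined analysis. SAP 2.1.2 also supplies an interval method for differences, though not a pooled one.
- **Redaction.** Protocol 9.4.3 has a redacted block after its subgroup list, and SAP 2.1.2 and 2.1.4 have others. The SAP reference list includes a paper on testing qualitative interactions and guidance on sex differences, neither cited in the visible text. They may belong elsewhere, such as the partly redacted centre-effect section. They do not show that an interaction analysis is planned, but they bar a claim that it is absent from the whole plan.
- **Consequence.** The analyses are descriptive, success rests on the primary test alone (SAP 1.6), and pooled intervals would still be wide.

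All of this stands, and it limits the point without removing it. SAP 2.3 is the sentence that says how the arms are compared, it says within each quintile, and the visible subgroup sections name nothing combined. Being exploratory excuses low power; it is no reason to prefer the less precise of two displays built on the same strata.

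**Conclusion.** The point holds as a matter of specification. SAP 2.3 prescribes within-quintile description, 2.3.1 to 2.3.3 use a phrase that allows another reading, and the visible text specifies neither a difference combined over quintiles nor a comparison between levels.

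Under the stated assumptions, pooling the same quintiles cuts the interval width to between about a third and a half of its within-quintile value. The absolute widths depend on the assumed rate, share and overlap; the relative gain depends only on overlap. The equal-share assumption is probably kind to the plan, because sex, age, diabetes and presentation are all on the propensity variable list in SAP 2.1.3.1, so subgroup levels may cluster in some quintiles and leave others thinner.

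Severity is low. Nothing here touches the primary test or trial success.

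**What to change.** In SAP 2.3, replace the within-quintile sentence with a statement that, for each subgroup level:

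- one NACE risk difference with a 95% interval will be reported, combined over the five overall-propensity quintiles with the stratum weights of the primary analysis (which the public text does not show);
- the difference between levels will be reported with its 95% interval;
- both are exploratory, and per-quintile counts will be given as a listing.

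Align the wording of 2.3.1 to 2.3.3 with this. State that the between-level interval will remain imprecise, at a half-width of about 6 points at a 10% rate, so that a null finding is not read as proof of consistency.

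The cost is the SAP wording and a rerun of the primary program by subgroup. No new data are needed.

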2.3.1 Sex

Sex-specific subgroup analyses will be performed on the primary analysis population for the primary endpoint stratified by the overall PS.

2.3.2 Diabetes

Diabetic subgroup analysis will be performed on the primary analysis population for the primary endpoint stratified by the overall PS. Analyses will be performed within the following subgroups:

- All diabetes mellitus, defined as any diabetics with or without medical treatment
- Non diabetes mellitus.

2.3.3 Other Subgroups

The following subgroups analyses will be evaluated for the primary analysis population for the primary endpoint stratified by the overall PS. Analyses will be performed within the following subgroups:

- Age (age \geq median vs $<$ median)
- Clinical presentation (ACS NSTEMI, ACS unstable angina, non-ACS)

2.4 Analysis Window

- 6 months
- 12 months

2.5 Handling of Missing Data

The primary analysis will be evaluated after propensity score stratification. To handle missing data in propensity score building, multiple imputation methods will be performed for baseline characteristics to compute propensity scores from these datasets.

All other analyses will be based on available data with missing data excluded. Any unused or spurious data will be noted as appropriate in the final report.

2.6.1 Multiple Center Effect

Analysis will be performed by pooling data across study sites.

The 1-month DAPT arm will have 50 sites globally. Subject registration is capped at 120 per site. This cap per site will prevent the scenario where the results from a few sites dominate the overall study result. For the analysis of center effect, data from smaller sites may be combined for the analysis. Smaller sites are defined as sites with fewer than 20 subjects per site.

[REDACTED]

[REDACTED]

[REDACTED]

[REDACTED]

[REDACTED]

2.7 Adjustments for Covariates

Unless otherwise specified, no adjustments for covariates will be made for any of the variables in the analyses.

2.8 Multiplicity Issues

No multiplicity adjustment is necessary because there is only one test on the primary endpoint

2.9 Sensitivity Analysis

The primary endpoint between 1-month and 6-month follow-up will be analyzed descriptively for the 1-month clear population removing the patients who do not have antiplatelet medication compliance after 1 month.

For the 1-month DAPT arm, antiplatelet medication non-compliance beyond 1-month follow-up for 1-month clear population is defined as patients who resume P2Y12 inhibitor for more than 7

consecutive days, and/or interrupt aspirin for more than 7 consecutive days between 1-month and 12-month follow up.

[REDACTED]

- [REDACTED]
- [REDACTED]

[REDACTED]

[REDACTED]

In addition, a sensitivity analysis will be performed for the primary endpoint analysis to evaluate the impact of the missing outcome. The analysis will be carried out based on the primary analysis population, and by imputing the missing outcomes for each imputed baseline PS dataset, and Rubin's combination rule ^[29] will be used to consolidate the final analysis for the 10 duplicates of the imputed dataset.

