**PROTOCOL ABT-CIP-10398 XIENCE 28 Global Study**

Point of Registration
	
Subject registration will occur after the index procedure but prior to discharge and up to 3 days post index procedure, upon confirmation of the following:
 
 • Signed informed consent has been obtained; • Subject has met all the inclusion and none of the exclusion criteria (including both general and angiographic criteria).

Subject Follow-Up
	
Subjects registered in the trial will receive the following clinical follow-up:
 
 • 1 month (28-35 days): office visit (Note: for subjects who have difficulty scheduling an office visit due to special circumstances, 1-month follow-up may be performed via telephone per physician's discretion) • 3 months (90 ± 7 days): office visit/telephone contact (office visit is strongly recommended whenever possible) • 6 months (180 ± 14 days): office visit/telephone contact (office visit is strongly recommended whenever possible) • 12 months (365 ± 28 days): office visit/telephone contact (office visit is strongly recommended whenever possible)

Primary Analysis Sample Size Justification
	
To further evaluate the safety of 1-month DAPT, non-inferiority (NI) will be tested comparing 1-month DAPT to XIENCE V USA historical control for the primary endpoint of NACE from 1- to 6-month follow-up in a "1-month clear" population (defined as subjects who are free from myocardial infarction [modified ARC], repeat coronary revascularization, stroke, or stent thrombosis [ARC definite/probable] within 1 month (prior to 1-month visit but at least 28 days) after stenting AND have been compliant with 1-month DAPT without interruption of either aspirin and/or P2Y12 receptor inhibitor for > 7 consecutive days).
 
[REDACTED]
 
[REDACTED]
 
[REDACTED]
 
[REDACTED]
 
[REDACTED]
 
[REDACTED]
 
[REDACTED]
 
[REDACTED]
 
[REDACTED]
 
[REDACTED]
 
[REDACTED]

PROTOCOL ABT-CIP-10398 XIENCE 28 Global Study

	
 • [REDACTED]

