1.3.3 Secondary Endpoint(s)

The following endpoints will be assessed from 1 to 6 months:

- Stent thrombosis (ARC definite/probable, ARC definite)
- All death, cardiac death, vascular death, non-cardiovascular death
- All myocardial infarction (MI) and MI attributed to target vessel (TV-MI, modified ARC)
- Composite of cardiac death or MI (modified ARC)
- Composite of all death or all MI (modified ARC)
- All stroke, ischemic stroke and hemorrhagic stroke
- Clinically-indicated target lesion revascularization (CI-TLR)
- Clinically-indicated target vessel revascularization (CI-TVR)
- Target lesion failure (TLF, composite of cardiac death, TV-MI and CI-TLR)
- Target vessel failure (TVF, composite of cardiac death, TV-MI and CI-TVR)
- Bleeding defined by the Bleeding Academic Research Consortium (BARC) type 2-5 and type 3-5

The primary endpoints of NACE and all the above secondary endpoints will also be assessed from 6 months to 12 months and from 1 month to 12 months, respectively.

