2.1.2 Descriptive Statistics for Categorical Variables

For categorical variables such as gender, NACE and TLF, results will be summarized with subject counts and percentages/rates, [REDACTED] with exact two-sided 95% Clopper-Pearson⁶ confidence intervals. Differences between two comparison groups of interest, when specified, will be summarized with the difference in percentages and the Newcombe⁵ score two-sided 95% confidence interval for the difference of two percentages.

For efficacy and safety endpoint(s), relative risks (i.e., the ratio of rates), confidence interval for the relative risks, the difference in rates and the confidence interval for difference in rates (using previously-described formulas), and p-values may also be presented for hypothesis generating purposes. The p-values will be based on either Pearson's Chi-square test or Fisher's exact test by checking the expected frequency for each cell in the 2x2 contingency table against Cochran's rule⁸, i.e., if the expected frequencies for all cells are ≥ 5 , then Pearson's Chi-square test will be used, otherwise Fisher's exact test will be used.

[REDACTED]

[REDACTED]

[REDACTED]

[REDACTED]

[REDACTED]

[REDACTED]

[REDACTED]

[REDACTED]

[REDACTED]

[REDACTED]

[REDACTED]

Formulas for calculating confidence intervals for the categorical variables are given below.

1. 100(1- α) % Exact Clopper-Pearson Confidence Interval for A Single Proportion⁶

$$\text{Lower Confidence Limit} = \frac{x}{x + (n - x + 1)F_{1-\frac{\alpha}{2}}(2(n - x + 1), 2x)}$$

$$\text{Upper Confidence Limit} = \frac{(x + 1)F_{1-\frac{\alpha}{2}}(2(x + 1), 2(n - x))}{n - x + (x + 1)F_{1-\frac{\alpha}{2}}(2(x + 1), 2(n - x))}$$

where:

n = sample size

x = number of "events"

$F_{1-\frac{\alpha}{2}}(df_1, df_2)$ = the (1- α /2) F - statistic for degrees of freedom df_1 and df_2

2. 100(1- α) % Newcombe Score Confidence Interval for the Difference of Two Proportions⁷

a. 100(1- α) % Wilson Score Confidence Interval for A Single Proportion⁵

$$\text{Lower Confidence Limit} = \left(\hat{p} + Z_{\alpha/2}^2 / 2n - Z_{\alpha/2} \sqrt{(\hat{p}(1 - \hat{p}) + Z_{\alpha/2}^2 / 4n) / n} \right) / (1 + Z_{\alpha/2}^2 / n)$$

$$\text{Upper Confidence Limit} = \left(\hat{p} + Z_{\alpha/2}^2 / 2n + Z_{\alpha/2} \sqrt{(\hat{p}(1 - \hat{p}) + Z_{\alpha/2}^2 / 4n) / n} \right) / (1 + Z_{\alpha/2}^2 / n)$$

where:

$$\hat{p} = x / n$$

n = sample size

x = number of "events"

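### The compliance sensitivity analysis of 1-6 month NACE removes 1-month DAPT subjects for drug changes up to month 12, after the endpoint window has closed

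*SAP*

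**What the plan says.** SAP 2.9 fixes the outcome window of this analysis: "The primary endpoint between 1-month and 6-month follow-up will be analyzed descriptively for the 1-month clear population", with subjects lacking antiplatelet compliance after month 1 taken out. For the 1-month DAPT arm, non-compliance "is defined as patients who resume P2Y12 inhibitor for more than 7" consecutive days and/or who "interrupt aspirin for more than 7 consecutive days between 1-month and 12-month follow up". Redacted lines follow directly.

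The Protocol Summary (Subject Follow-Up) and Protocol 6.4 place the 1-month visit at days 28-35. The later visits are "6 months (180 ± 14 days): office visit/telephone contact" and "12 months (365 ± 28 days): office visit/telephone contact".

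SAP 1.3.3 states that NACE and the secondary endpoints "will also be assessed from 6 months to 12 months and from 1 month to 12 months, respectively". The visible text of SAP 2.9 applies the compliance definition only to NACE from 1 to 6 months.

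The primary analysis is separate. SAP 2.2.1 says "A non-inferiority test will be performed on the primary endpoint between 1-month and 6-month follow up for the primary analysis population", and SAP 1.6 defines trial success by that test alone.

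**The concern.** The purpose of the analysis is to describe 1-6 month NACE in subjects who kept to the regimen. For that endpoint, what matters is adherence up to month 6. As written, a subject who adhered fully through month 6 and resumed a P2Y12 inhibitor at, say, month 9 is dropped, along with whatever happened to them in months 1-6.

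This selects subjects on information from after the outcome window, in two ways that need not balance:

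- A subject who died by month 6 had an event and cannot be removed for a late change, whereas survivors can. This pushes the rate up.
- A non-fatal event in months 1-6 may lead to a drug change after month 6. That subject and the event are then removed, which pushes the rate down.

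At stake is how readers interpret one descriptive rate that is meant to support the primary result.

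**Working it through.** The plan states no figure for this analysis, and the visible text gives no event rate or drug-change frequency. Only the window comparison rests on the documents alone. Everything after step 1 is illustration on stated assumptions.

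**1. Windows.** Inputs: day 28 (the earliest day of the 28-35 day visit), day 180 and day 365, from Protocol 6.4.

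- Removal window: 365 − 28 = 337 days.
- Part after the endpoint closes: 365 − 180 = 185 days.
- Share: 185/337 = 54.9%.
- Starting at day 35 instead: 185/330 = 56.1%.
- Using the latest allowed 6- and 12-month visits (days 194 and 393): (393 − 194)/(393 − 28) = 199/365 = 54.5%.

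Visit windows do not explain the difference.

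**2. Effect of removing late changers only.** Let p be the 1-6 month NACE rate in subjects adherent through month 6. Let f be the share of them who change drugs only after month 6, and RR their 1-6 month NACE risk relative to p. Removing them shifts the rate by

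p(1 − f·RR)/(1 − f) − p = p·f(1 − RR)/(1 − f).

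With p = 10% and f = 5% (both assumed):

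| RR | Shift (percentage points) |
|---|---|
| 0 | +0.53 |
| 0.5 | +0.26 |
| 1 | 0 |
| 2 | −0.53 |

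Over p = 6-15%, f = 2-10% and RR = 0-2, the shift runs from −1.67 to +1.67 points; the extremes are 0.15 × 0.10/0.90 = 0.0167. Because p refers to subjects who kept to the regimen through month 6, this shift is an error relative to what the analysis sets out to describe.

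**3. Changes unrelated to events, with deaths the only difference.** Assumptions:

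- The true rate is 10%, and drug changes do not alter risk.
- Changes occur at a constant rate, so that 10% of event-free subjects qualify over the 11 months.
- Event times are uniform over months 1-6.
- A share q of events is fatal.

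By month 6, 1 − 0.9^(5/11) = 4.68% of event-free subjects qualify, so (10 − 4.68)/10 = 53% of their removals are for late changes.

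The monthly rate of change is h = −ln(0.9)/11 = 0.00958. A subject with a fatal event qualifies before death with average probability 1 − (1 − e^(−5h))/(5h) = 2.36%. Event subjects are therefore removed with share F = 10%(1 − q) + 2.36%·q under the 12-month rule, or 4.68%(1 − q) + 2.36%·q under a 6-month rule. The event-free share removed is g = 10% or 4.68%. The reported rate is 0.1(1 − F)/[0.1(1 − F) + 0.9(1 − g)].

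| q | F, 12-month rule | Reported, 12-month rule | F, 6-month rule | Reported, 6-month rule |
|---|---|---|---|---|
| 0% | 10.00% | 10.00% | 4.68% | 10.00% |
| 20% | 8.47% | 10.15% | 4.21% | 10.04% |
| 40% | 6.94% | 10.30% | 3.75% | 10.09% |

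Under these assumptions the upward shift is at most 0.3 points, and ending the window at month 6 removes most of it.

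**The case against.** **The month-12 limit may belong only to the aspirin clause.** Grammatically that is the most direct reading. P2Y12 resumption would then have no stated end date, so the mismatch remains. The 55% applies directly to aspirin only.

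**One definition may be meant to serve several endpoints.** The regimen runs through 12 months, NACE is also assessed from 1 to 12 months, and SAP 2.4 lists both 6 and 12 months. This is a plausible origin for the wording, and the longer window suits a 1-12 month endpoint. It does not cure the visible pairing with the 1-6 month endpoint.

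**The redacted lines may contain more.** This stands as a limit. They may hold an ordering rule, an endpoint-specific window or a control-arm rule. Nothing can be inferred about them, and no claim is made here about the control arm. A reader might infer that the plan lacks any rule for drug changes made after an event; the documents do not support stating that as a defect.

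**A lower rate after removal need not be bias.** This also stands. A reader might take any excess removal of event subjects as downward bias, and equal removal shares as proof of none. Neither follows. If a drug change before month 6 alters risk, the rate in adherent subjects really does differ from the rate in all 1-month clear subjects, and showing that difference is the purpose of the analysis. Only selection on late changes, or on changes that follow the event, is an error.

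**Readers will see the counts.** SAP 2.1.2 provides that "For categorical variables such as gender, NACE and TLF, results will be summarized with subject counts and percentages/rates", so the overall shares removed can largely be recovered by comparison with the primary population. Counts do not show whether a change came before or after month 6, or before or after the event.

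**Conclusion.** The point holds on the visible text: a 1-6 month endpoint is paired with a removal rule that uses drug changes up to month 12, and about 55% of the days in that rule come after the endpoint has closed. A reader might take this to mean that 55% of removals are for late changes, but that would need drug-change frequencies the documents do not give.

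The direction and size of any bias are unknown. On the assumptions in step 3 it is zero or slightly upward. Step 2 shows that it could go either way if late changers had a different earlier risk.

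A reader might also infer that the trial's conclusion is at risk. It is not: the analysis is descriptive, and the non-inferiority test in SAP 2.1.4 and the success criterion in SAP 1.6 do not use it. The severity is minor. Confidence is high that the visible windows do not match; what the redacted lines say is unknown.

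**What to change.** In SAP 2.9, for NACE from 1 to 6 months, end the non-compliance window at 6-month follow-up for both P2Y12 resumption and aspirin interruption. Keep the 12-month window only where a 1-12 month endpoint is analysed.

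If the redacted lines hold no ordering rule, add that a drug change starting after a subject's first NACE event does not remove that subject. Censoring at first non-compliance with the Kaplan-Meier method of SAP 2.1.5 is an optional alternative, not a requirement. If it is chosen, the SAP should acknowledge that the censoring may be informative.

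The cost is SAP wording and programming. Protocol 6.3.2 already has antiplatelet start and stop dates recorded in the eCRF, so no new data are needed.
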